4.4. Subject withdrawal criteria.

Will be removed from the study:

- to. Any patient who presents hypercalcemia during the controls carried out throughout the trial.
- b. Subjects who present with ECG abnormalities indicative of possible hypercalcemia or arrhythmias during treatment with calcitriol.
- c. Those who repeatedly skip taking treatment.
- d. Those affected who present a new disease or require supplementary treatment that may make the interpretation of the results difficult.

Patients with hypercalcemia and those with ECG abnormalities will continue to be monitored until resolution of symptoms or recorded abnormalities (see Addendum 6).

Telephone or email contact will also be maintained with the patients in section d), although they will not re-enter the study.

Controls with those in section c) will not be followed.

A notification of a serious adverse effect will be made if this occurs (see Addendum 7).

The date of withdrawal from the study and the reason for this, as well as the evolution followed by the patient, will be noted in the CRD.

Subjects who drop out of the study will not be replaced by others as long as the "n" of the study remains between 15 and 20.

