9. STATISTICS

9.1 Sample size for a pilot study.

Number of subjects planned: 20

Given the type of study design, a formal calculation of the sample size is not required.

However, general rules for determining the appropriate sample size for a pilot study have been described in the scientific literature. For two-arm studies, it is recommended to recruit between 24-40 patients in total. For single-group studies, the calculation can be adapted by applying an adjustment factor of 0.5. Therefore, in our study it is estimated that it will be necessary to recruit a minimum of between 15-25 patients, assuming a loss rate of 20%.

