9.2 Statistics methods

A descriptive analysis will be carried out using the usual statistics: mean and standard deviation, or median and interquartile range for quantitative variables with non-normal distribution. The normality of the data will be checked using the Shapiro-Wilks test and/or Q-Q plots. The qualitative variables will be described according to the number and percentage of subjects in each category.

The effect of treatment with calcitriol on neurological function will be evaluated using a mixed linear model with the levels of neurological function tests as a dependent variable and the measurement time (screening, 6-month control and final control) as an independent variable included as an effect. random. To take into account possible confounding effects, covariates will be introduced as fixed effects. The same analysis will be repeated for frataxin levels and other biochemical parameters in platelets.

Comparison of baseline frataxin levels between healthy controls and patients with ataxia will be carried out using the Student's t test for independent data or the Mann-Whitney U test, if the data do not meet the assumption of normality. The relationship between the increase in frataxin production and clinical improvement will be

evaluated using a logistic regression model where the dependent variable will be defined dichotomously by jointly evaluating frataxin levels against increases of more than one point on the scale. SARA, two or more points of the SCAFI composite index (which would add the results of the 8 m walk test, time taken from the 9-HPT, the number of syllables from the PATA test), the values of the Barthel Index in 10% and the SF36 questionnaire by 20% on the values obtained in the first evaluation.

The results will be expressed in odds ratio (OR).

The effect of treatment with calcitriol on the quality of life of the patients at the beginning and end of treatment will be evaluated through the t-student test for paired data or the Wilcoxon test, if normality is not met in the distribution of the data.

To assess toxicities, a table of frequencies of occurrences will be created.

Statistical analysis will be performed with o IBM SPSS Statistics version 26 and R software.

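### The frataxin–clinical link is tested only by logistic regression on a yes/no outcome in about 15–20 patients, giving up roughly a third to more than half of the power of the continuous changes already collected

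*Combined protocol and SAP*

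**What the plan says.** Section 9.2 states that the link between frataxin production and clinical improvement will be "evaluated using a logistic regression model where the dependent variable will be defined dichotomously" and that results will be given as odds ratios. The yes/no variable is built "by jointly evaluating frataxin levels against increases of more than one point on the scale", that scale being SARA, with further cut-offs of two or more points on SCAFI, 10% on Barthel and 20% on SF36. The section does not say whether all or any of these must be met, which test of the odds ratio will be used, or in what form frataxin enters as predictor.

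On numbers, section 9.1 gives "Number of subjects planned: 20" and "a minimum of between 15-25 patients, assuming a loss rate of 20" per cent. Section 4.4 does not replace dropouts while the sample size "remains between 15 and 20".

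On data, section 3.4 has frataxin measured at baseline, 15 days, 4, 8 and 12 months. Section 6.2 has neurological function measured at baseline, 6 and 12 months. Section 6.1 lists the frataxin increase from baseline as an efficacy variable. The mixed model in section 9.2 keeps the tests continuous, but its stated explanatory variable is time. No regression or correlation of frataxin change with clinical change is planned.

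**The concern.** Frataxin, SARA and the SCAFI components are all measured as quantities. Cutting clinical change into responder and non-responder treats a patient just over the cut-off like one far beyond it, and the information lost cannot be recovered by repairing the definition or the cut-offs. With so few patients, the logistic model adds a small-sample problem: there may be no responders, or responders and non-responders may be completely separated by frataxin, and then no finite odds ratio exists.

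The trial rests on the idea that raising frataxin could modify neurological function (section 2.1), and this is the only planned analysis that examines that step within patients. Section 1 says positive results would lead to larger trials. An avoidably weak test, or an odds ratio that cannot be estimated, would inform that decision poorly.

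**Working it through.** **1. The plan's own sample-size figure.** Section 9.1 starts from the two-arm guidance that "it is recommended to recruit between 24-40 patients in total" and adapts it by "applying an adjustment factor of 0.5". 24 × 0.5 = 12 and 40 × 0.5 = 20. Allowing for 20% loss, 12 / 0.8 = 15 and 20 / 0.8 = 25. The stated 15–25 is reproduced. With 20 enrolled and 20% lost, 20 × 0.8 = 16 remain, so 16 and 20 are used below. No power is stated for the frataxin–clinical analysis, so there is none to reproduce.

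**2. Assumptions not in the documents.** Frataxin change and clinical change are bivariate normal with correlation ρ (0.3–0.7 examined; main case 0.5). The responder share is 10–50%. The outcome is purely clinical, frataxin change is a continuous single predictor, and two-sided alpha is 0.05.

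**3. Information kept by a cut, large samples.** The fraction kept is φ(c)² / [p(1 − p)], where p is the responder share, c the normal cut-off giving that share and φ the normal density. At p = 50%, 0.3989² / 0.25 = 0.64. At 30%, 20% and 10% it is 0.58, 0.49 and 0.34.

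**4. Small-sample power by simulation** (20,000 trials per setting, ρ = 0.5). Separated fits count as not significant for Wald. The likelihood-ratio (LR) statistic is still defined under separation and is scored as such. Calibrated LR means the critical value was set to give true 5% size.

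| Test | Responders 50% | 30% | 20% | 10% |
|---|---|---|---|---|
| n = 16, continuous (Pearson) 53% | | | | |
| Wald | 9% | 6% | 2% | <1% |
| LR, uncalibrated | 41% | 38% | 33% | 25% |
| LR, calibrated | 35% | 31% | 27% | 19% |
| n = 20, continuous (Pearson) 65% | | | | |
| Wald | 27–28% | 19–20% | 10% | 2% |
| LR, uncalibrated | 49% | 45% | 39% | 29% |
| LR, calibrated | 43% | 39% | 31% | 22% |

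Ranges show agreement between two separate simulations. Uncalibrated LR has a type I error of about 6.5–8%, so its rows flatter it. Wald's is below 2.5%.

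**5. Relative loss, 1 − (logistic power / continuous power), from unrounded powers.**
- Calibrated LR, n = 16: 1 − 0.347/0.530 = 34% at 50% responders, then 42%, 50% and 64%.
- Calibrated LR, n = 20: 1 − 0.428/0.645 = 34%, then 39%, 52% and 66%.
- Wald, across both sample sizes: from 1 − 0.281/0.645 = 56% to 1 − 0.004/0.535 = 99%.

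**6. Trials with no usable odds ratio.** At 10% responders, the chance of no responder is 0.9¹⁶ = 18.5% (n = 16) or 0.9²⁰ = 12.2% (n = 20). Simulated separation adds 11.7% and 8.8%, giving about 30% and 21%. At 30% responders and n = 16 the total is 0.3% + 2.4% = 2.7%. At 50% it is under 1%.

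**7. What the continuous analysis delivers.** By Fisher's z, n for 80% power is [(1.960 + 0.842) / atanh ρ]² + 3. This gives 29.0, so 30, at ρ = 0.5, and 19.3, so 20, at ρ = 0.6. Power is only 21% (n = 16) to 26% (n = 20) at ρ = 0.3. Spearman at ρ = 0.5 has 46% and 57%. For an observed correlation of 0.5, the 95% CI is tanh(0.549 ± 1.96/√(n − 3)), that is 0.01 to 0.80 with 16 patients and 0.07 to 0.77 with 20.

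**The case against.** Section 9.1 says that a pilot needs no formal sample-size calculation, and this is not the primary analysis, so power may seem the wrong yardstick. That is fair as to weight, but it favours the change: a pilot's useful product is an estimate with an interval, and a slope or correlation is available in essentially every trial while an odds ratio may not be.

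The figures also describe a cleaner analysis than the one written. Section 9.2 appears to place frataxin inside the dependent variable and leaves the predictor unclear. This stands as a limit on the percentages. If frataxin were itself split at its median (Fisher's exact test, ρ = 0.5, 30–50% responders), power would be 14–17% with 16 patients and 16–20% with 20.

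Three stronger readings are tempting, and the documents do not support any of them in general:
- *Most of the power is always lost.* Section 9.2 names no test. With a correctly sized LR test and 30–50% responders the loss is about a third to two fifths. Even Wald at ρ = 0.7, n = 20 and 50% responders keeps 56% against 96%.
- *The odds ratio will often be inestimable.* This needs few responders. A low share is plausible if every criterion must be met, since SCAFI is a composite Z-score (section 6.1) and two points is then a large change. But section 9.2 does not say that all are required.
- *A strong relation would be reported as absent.* At ρ = 0.5 every logistic variant has under 50% power. At ρ = 0.7 and n = 20, however, the calibrated LR test has 73–79% with 30–50% responders.

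**Conclusion.** The point holds at this size: dichotomising gives up roughly a third to more than half of the power available from the continuous changes, and most of it under the usual Wald test in nearly all scenarios, or under any of these tests once about 20% or fewer respond with a correctly sized comparison. The continuous analysis was better in every scenario examined. If only about 10% respond, some 30% of trials with 16 patients, or 20% with 20, would yield no usable odds ratio. With 30–50% responders this is at most about 3%.

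The direction of this conclusion is secure. Its exact size rests on an assumed correlation, an assumed responder share, normal changes, and a clinical-only outcome with continuous frataxin as predictor. It does not follow that the continuous analysis makes the study well powered: at ρ = 0.5 with 16 patients it still misses the relation 47% of the time.

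**What to change.** In section 9.2, replace the logistic model as the main analysis of this link with a linear regression (or Spearman correlation, if the distribution requires it) of each patient's 12-month change in SARA on that patient's 12-month change in frataxin from baseline. Report the slope or correlation with its 95% CI. Name SARA as the leading outcome, do the same for SCAFI as a supporting analysis, and for Barthel and SF36 if wanted. State for each scale which direction of change is improvement. Keep the responder classification as a descriptive table only, with frataxin removed from its definition and the all-or-any rule stated.

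The cost is wording: no extra patients, visits or samples. The downside is that no odds ratio is reported. The plan should also say that this analysis is for estimation and is not a definitive test, given its imprecision at these numbers.

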3. TRIAL DESIGN

Given the purpose of the trial, the neurological function of the patients will be evaluated prior to the start of treatment, at 6 months and at 12 months. The duration is determined by the characteristics of the disease, which is neurodegenerative and therefore changes in neurological function are not expected until after a long period of time. Neurological function will be assessed using standardized tests aimed at assessing cerebellar motor function, gait, dysarthria and manual dexterity. This includes the SARA scale for assessing and grading cerebellar function, the eight-meter walk test (time taken by the patient to travel 8 meters in both directions and calculating round trip and average), a dexterity test, the 9-Hole Peg test (the time spent placing nine pegs in 9 holes, with the dominant and non-dominant hand, is assessed, and the PATA speed test, for assessing dysarthria, in which the number of times is counted that the patient emits these syllables in two periods of 10 seconds, calculating the number in each series and the average of both).

All these tests will be videotaped and the files obtained will be archived on an external hard drive for conservation, evaluation, reproduction and subsequent comparison. In this first visit, measures of activities of daily living will be taken using the Barthel Index and also the SF36 questionnaire (Spanish version of SF-36v2™).

Control visits will be made at 15 days, 4, 8 and 12 months, to check calcium levels (among other analytical determinations), symptoms of adverse effects, and ECG. Communication with patients will be facilitated with various methods (telephone, email) to assist them in any eventuality.

In these same visits and with the same extraction, samples will be obtained to determine frataxin levels. Frataxin will be quantified by western blot of platelet lysate.

In the same lysate, various mitochondrial proteins will be quantified by SRM-based mass spectrometry.

3.1 Specific description of the main and secondary variables.

As primary variables, the parameters obtained from the aforementioned neurological function tests will be specifically evaluated: SARA scale values, time to travel 8 meters, time to complete the 9-hole test, number of syllables of the dysarthria test.

Secondary variables will be evaluated: calcium levels and kidney function, frataxin levels, Barthel index values and SF36 quality of life questionnaire.

3.2 Description of the type of trial.

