6. ASSESSMENT OF EFFICACY

6.1 Specification of efficacy variables.

The efficacy variables for improving neurological function would be the initial, intermediate and final comparison of:

- Partial and total values of the SARA scale (Scale for the assessment and grading of cerebellar function in ataxias).
- SCAFI index (composite Z-score) result of the transformation of the results of:
 - .. Average time to travel 8 meters round trip.
 - .. Time spent completing the 9-hole test with dominant and non-dominant hands.
 - .. Number of syllables PA-TA repeated in two series of 10 seconds.
- Total partial scores of the Barthel Index.
- Total score and each dimension of the SF36 quality scale.
- Increase in frataxin levels compared to baseline measurement figures.
- Significant change in the values of the mitochondrial proteins studied.

6.2 Methods and schedule for evaluation, registration and analysis of efficacy parameters.

- Evaluations of efficacy parameters will be carried out at the beginning, after 6 months and after one year of treatment for neurological function. The quality of life questionnaire and the Barthel index will be administered at the screening visit and after one year of treatment.
- The registration of these data will be carried out in the corresponding CRD.

- The parameters will be assessed and compared at the end of the study.

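### Sections 6.1 and 9.2 define SCAFI differently, and neither fixes its direction, reference values or the unit of its two-point cut-off

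*Combined protocol and SAP*

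**What the plan says.** Section 6.1 (Specification of efficacy variables) lists the "SCAFI index (composite Z-score) result of the transformation of the results of" three tests:

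- Walking, where lower is better: "Average time to travel 8 meters round trip"
- Dexterity, where lower is better: "Time spent completing the 9-hole test with dominant and non-dominant hands"
- Speech, where higher is better: "Number of syllables PA-TA repeated in two series of 10 seconds"

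It does not state the transformation, the sign given to the two times, the mean and SD used for standardising, how the two hands are combined, or whether the Z-scores are summed or averaged.

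Section 9.2 (Statistics methods) describes the same index in a parenthesis: "SCAFI composite index (which would add the results of the 8 m walk test, time taken from the 9-HPT, the number of syllables". It appears in the analysis that relates frataxin increase to clinical improvement. That relation is to be "evaluated using a logistic regression model where the dependent variable will be defined dichotomously". The definition of the outcome then reads "jointly evaluating frataxin levels against increases of more than one point on the scale. SARA, two or more points of the SCAFI composite index", and it goes on to include Barthel and SF36 changes. No unit is attached to the points.

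Section 3.1 names the primary variables as "SARA scale values, time to travel 8 meters, time to complete the 9-hole test, number of syllables of the dysarthria test". SCAFI is not among them.

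**The concern.** The two descriptions lead to different scores. A sum of results mixes seconds, seconds and a count; a Z-score has no units. Addition also joins two measures on which lower is better to one on which higher is better, and the only combination rule the plan states is that addition. A score built this way has no consistent direction of benefit, so a rise in it cannot be read as improvement.

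The stake is greatest in the logistic regression, where a rise of at least two points counts as clinical improvement. Under a raw sum, a patient whose peg time lengthens by 2 s with the other tests unchanged meets that part of the rule. The protocol itself describes the disease as progressive, so lengthening times over a year are a realistic pattern.

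A second stake is analyst freedom. The study is open-label with one arm. If sign, reference values and scaling are chosen after the data are seen, nothing in the plan limits that choice.

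**Working it through.** **The plan's own figures.** The plan gives no figure for SCAFI: no component means, SDs or expected change. The only derived figure in the statistics section, the recruitment range in 9.1, reproduces and is unaffected: 24 × 0.5 / (1 - 0.20) = 15 and 40 × 0.5 / (1 - 0.20) = 25.

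**Step 1: algebra, with no assumed values.** Let every test improve by d SD. In Z units, walk time changes by -d, peg time by -d and PATA by +d.

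- Unaligned: sum = -d - d + d = -d; mean = -d/3.
- Both times sign-reversed: sum = d + d + d = +3d; mean = +d.
- At d = 0.5 the means are -0.17 and +0.5. The unaligned score has the wrong sign and one third of the size.
- Exact cancellation is possible. Changes of -0.5, -0.5 and +1.0 SD sum to 0 unaligned, but to 0.5 + 0.5 + 1.0 = 2.0 aligned.

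**Step 2: raw sum, with assumed baseline values.** The means and SDs below are assumptions, so three sets are shown. Each test improves by 10% of its mean.

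| Assumed mean (SD): walk s; pegs s; PATA | Raw-sum change | Unaligned Z sum | Aligned Z sum |
|---|---|---|---|
| 8 (3); 50 (15); 20 (5) | -0.8 - 5.0 + 2.0 = -3.8 | -0.20 | +1.00 |
| 12 (6); 70 (30); 18 (5) | -1.2 - 7.0 + 1.8 = -6.4 | -0.07 | +0.79 |
| 6 (1.5); 40 (10); 25 (6) | -0.6 - 4.0 + 2.5 = -2.1 | -0.38 | +1.22 |

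The Z columns divide each change by its SD. For the first row, -0.8/3 - 5.0/15 + 2.0/5 = -0.20; with the times reversed, 0.27 + 0.33 + 0.40 = 1.00.

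A 10% worsening on every test reverses the raw changes to +3.8, +6.4 and +2.1. All three meet a two-point increase.

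**Step 3: weight of the components in a raw sum.** If the tests are taken as uncorrelated, the peg test's share of the variance is 225/(9 + 225 + 25) = 87% in the first set, 900/(36 + 900 + 25) = 94% in the second and 100/(2.25 + 100 + 36) = 72% in the third. A raw sum would be largely a peg-time score.

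**Step 4: what two points means once direction is aligned.**

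- Z-scores summed: 3d = 2, so d = 2/3 = 0.67 SD per test.
- Z-scores averaged: d = 2 SD per test.

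In the first assumed set, a 10% gain on all tests gives an aligned sum of 1.00 and a mean of 0.33. Scaling these linearly, two points needs about a 20% gain on every test if summed (2/1.00 × 10%) and about 60% if averaged (2/0.33 × 10%). The choice between sum and mean therefore changes the cut-off threefold.

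**The case against.** The strongest defence is that 6.1 is the section that specifies the efficacy variables, and it says the index comes from a transformation. That could include inverting or sign-reversing the times, and if it does, nothing cancels or reverses. The wording in 9.2 is a parenthesis in a sentence about something else, in a rough translation (7.2 still contains an untranslated Spanish phrase), so it may be meant only as a list of components. Section 3.4 also refers to Addenda 5.1 to 5.4 for the assessments at the final visit. They are not in the supplied text and may hold a scoring rule.

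Much of this stands. A reader might infer that real gains will necessarily cancel or reverse; the documents do not support that, because it depends on which description is applied. A reader might also fear that each visit will be standardised on its own data, which would force the cohort mean to zero every time; no section proposes this. Nor do the primary variables depend on SCAFI, since 3.1 names SARA and the tests separately and they can be analysed without the composite.

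The defence does not remove the inconsistency. Section 9.2 names the time taken on the peg test as one of the things added, and it is the section that applies the cut-off. A scoring rule in an addendum would still conflict with that wording, and the two-point threshold would still need a unit.

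**Conclusion.** The point holds as an inconsistent and incomplete definition, with a conditional risk of a wrong-direction score. If 9.2 is followed as written, or Z-scores are combined unaligned, an equal gain of d SD on each test appears as a mean of -d/3 rather than +d. This needs no assumed values beyond equal gains in SD units. The raw-sum results, a fall of 2.1 to 6.4 points for a 10% gain and a rise of the same size for a 10% worsening, rest on the assumed means; the peg-test share of 72% to 94% also assumes uncorrelated tests.

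The damage is confined to SCAFI as an efficacy variable and to the logistic-regression outcome that uses it. It does not extend to the primary tests in 3.1, and the documents do not show that reversal will occur. Because the cut-off's meaning also depends on sum versus mean (0.67 or 2 SD per test), both the score and its threshold should be settled before any analysis.

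**What to change.** Use one definition of SCAFI in 6.1 and 9.2, with a single transformation rather than a choice between alternatives. For example:

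- At every visit, convert walk time, peg time (mean of both hands) and PATA count to Z-scores using this cohort's baseline mean and SD.
- Reverse the sign of the two times, average the three Z-scores, and state that higher is better.
- Delete the parenthesis in 9.2 that describes the index as an addition of results.
- Restate the two-point SCAFI cut-off in the units of the chosen score. Carrying it over unchanged to an averaged Z-score would require a mean gain of 2 SD per test.

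If an addendum already holds a scoring rule, cite it in 6.1 and make 9.2 agree with it. The cost is a few lines of wording; no new data, visits or tests are needed.

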The ideal dose of calcitriol to raise frataxin levels in patients with Friedreich's ataxia is unknown. Levels of the precursor (25-OH-VitD, known as calcidiol) are below normal in patients with Friedreich's ataxia (Eigentler et al, 2014), but it is not possible to determine calcitriol levels in this research. Therefore, the most prudent option is, in this first study, to use a low dose of calcitriol and check if this is sufficient to raise frataxin levels, in addition to carefully and repeatedly measuring calcemia levels to control possible adverse effects of treatment. This will therefore be the first "in vivo" study in which the possible effect of calcitriol on the production of frataxin in patients with a severe deficit in its production will be analyzed and will allow to know on the one hand the tolerability and safety of the drug in these patients and if a low dose is sufficient to induce changes in neurological function. A single daily dose of 25 micrograms of calcitriol will therefore be used throughout the study treatment period (12 months).

1.5 Description of the population to be studied.

The effects of calcitriol on the neurological function of patients with FA will be studied, among this population will be selected patients who still retain ambulatory capacity, that is, patients who do not yet have a significant degree of disability.

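### The percentage cut-offs for Barthel and SF36 cannot be met from high baselines and the SCAFI cut-off has no fixed meaning, so responder status in section 9.2 depends partly on how well the patient starts

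*Combined protocol and SAP*

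**What the plan says.** Section 9.2 dichotomises the outcome of a logistic model by setting frataxin levels against four clinical changes: SARA by more than one point, SCAFI by "two or more points of the SCAFI composite index (which would add the results of the 8 m walk test" and the other component tests), and changes in "the values of the Barthel Index in 10% and the SF36 questionnaire by 20% on the values obtained in the first evaluation". It does not say whether one, several or all four must be met. It also does not say which SF36 score carries the 20% rule, although section 6.1 lists both a total and each dimension.

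Section 6.1 describes SCAFI differently, as "SCAFI index (composite Z-score) result of the transformation of the results of" the walk, peg and syllable tests.

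Section 1.5 aims at "patients who still retain ambulatory capacity, that is, patients who do not yet have a significant degree of disability". Section 4.1 admits anyone aged 16 to 65 with genetically confirmed disease who can walk, with whatever support, and sets no entry limit on any of the four scales. Section 9.1 gives the size: "Number of subjects planned: 20".

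**The concern.** A patient near the top of a bounded scale has little or no room for a percentage gain, and the gain demanded in points grows with the starting value. The population described in section 1.5 is one in which high Barthel scores are plausible. Responder status would then reflect starting severity as well as response to calcitriol.

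The SCAFI cut-off raises a different problem. Its size depends on how the index is built, and sections 6.1 and 9.2 do not describe it in the same way.

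This is the only planned analysis that connects the biomarker with clinical benefit. If few or no patients can be classed as responders, no usable odds ratio results. If the classification partly tracks baseline severity, the odds ratio is hard to interpret. Section 9.2 states no baseline adjustment for this model.

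**Working it through.** **The plan's own figure.** Section 9.1 starts from "For two-arm studies, it is recommended to recruit between 24-40 patients in total", says "the calculation can be adapted by applying an adjustment factor of 0.5", and sets the range "assuming a loss rate of 20" per cent. 24 × 0.5 = 12 and 12/0.8 = 15; 40 × 0.5 = 20 and 20/0.8 = 25. The stated 15-25 reproduces. With 20 enrolled, 20 × 0.8 = 16 are evaluable. The plan gives no responder rate or baseline distribution.

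**Ceilings.** On a scale with maximum M, a relative rise r is possible only from a baseline of at most M/(1 + r). Assume Barthel 0-100 in steps of 5 and SF36 0-100.
- Barthel: 100/1.10 = 90.9.
- SF36: 100/1.20 = 83.3.

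| Scale | Baseline | Score needed | Reachable |
|---|---|---|---|
| Barthel | 85 | 93.5, so 95 | yes |
| Barthel | 90 | 99, so 100 | only with a perfect score |
| Barthel | 95 | 104.5 | no |
| Barthel | 100 | 110 | no |
| SF36 | 30 | 36 (gain of 6) | yes |
| SF36 | 80 | 96 (gain of 16) | yes |
| SF36 | 85 | 102 | no |

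If 25%, 50% or 75% of 20 patients started at a ceiling (assumed range), 5, 10 or 15 could not meet that criterion.

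**SCAFI.** A gain of 2 needs an average shift of 2 SD per test if the index is a mean of three Z-scores, and 2/3 = 0.67 SD per test if it is a sum. Assume a baseline-to-follow-up correlation ρ of 0.8-0.9 and a correlation c of 0-0.5 between component changes. The SD of change in the mean is √(2(1 − ρ)) × √((1 + 2c)/3):
- ρ = 0.9, c = 0: 0.447 × 0.577 = 0.26.
- ρ = 0.8, c = 0.5: 0.632 × 0.816 = 0.52.

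For the sum, multiply by 3: 0.78 to 1.55. The chance of a gain of 2 or more is then:

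| Reading | No true effect | True gain of 0.5 SD per test |
|---|---|---|
| Mean of Z-scores | below 0.01% | below 0.2% |
| Sum of Z-scores (true gain 3 × 0.5 = 1.5) | about 0.5% to 10% | about 26% to 37% |

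With a wider assumed SD of change in the mean (0.3-0.8) and a true gain of 0-0.5, the ranges are about 0-3% for a mean and 1-42% for a sum. If raw results were added, times (lower is better) would be combined with syllable counts (higher is better). With an assumed change SD of 3 to 8 units and no effect, P(Z > 2/3) = 25% and P(Z > 2/8) = 40% would pass by chance.

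**Combination rule.** Take illustrative, independent rates: SARA 40%, Barthel 15%, SF36 20%, SCAFI 1% (mean) or 20% (sum).
- All four required: 0.40 × 0.15 × 0.20 × 0.01 = 0.012%, or 0.24% with SCAFI at 20%. The chance of no responder among 16 is 0.99988^16 = 99.8% or 0.9976^16 = 96%.
- Any one sufficient: 1 − 0.60 × 0.85 × 0.80 × 0.99 = 60%, or 67% with SCAFI at 20%; about 10 to 11 of 16.
- Any one sufficient, patient at both ceilings: 1 − 0.60 × 0.99 = 41%, or 1 − 0.60 × 0.80 = 52%. Such a patient has fewer routes to response than one with room to improve (60% or 67%).

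**Information left after dichotomising.** Simulated power of the logistic likelihood-ratio test (two-sided 0.05, assumed odds ratio 3 per SD of frataxin rise, 800 runs) is 8% at a 2% responder rate and 50% at a 50% rate with 16 patients. With 20 patients it is 8% and 57%.

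**The case against.** A reader might infer that many patients cannot respond and that the link with frataxin cannot be tested. The documents do not support this. They give no baseline Barthel or SF36 data, and section 4.1 admits patients who walk with any support, some of whom may start at Barthel 90 or below. In section 9.2 the notion of joint evaluation ties frataxin to the clinical changes; it does not require all four criteria. Under an any-criterion rule the model can be fitted.

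A reader might also infer that the SCAFI cut-off is out of reach. A Z-score has no ceiling, section 6.1 never specifies a mean, and a sum of Z-scores fits both sections and makes a gain of 2 attainable. The SARA criterion is not touched by the ceilings at all.

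Further, the trial is a 20-patient pilot, and the frataxin-clinical relation is not listed as an objective in sections 2.1 or 2.2. A model without responders would fail visibly and need not pass for evidence of no relationship.

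All of this stands and limits the point. It does not remove the ceilings or settle what two SCAFI points mean. Stating an any-criterion rule would still leave patients at a ceiling with fewer ways to be counted as improved.

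**Conclusion.** The point holds in a limited form and is a should-fix. On the assumed scale ranges, the Barthel criterion is unreachable from 95 or 100 and the SF36 criterion above 83.3. The SCAFI cut-off varies threefold in SD per test between a mean and a sum of Z-scores. Under either combination rule, responder status depends partly on baseline severity. Under an all-criteria rule patients at a ceiling can never respond, and an odds ratio may not be estimable; under an any-criterion rule the model can be fitted but is distorted.

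How many patients are affected is unknown. The scale ranges, correlations, change SDs and component rates are assumptions. The mixed models for neurological function and frataxin, and the paired tests for quality of life, do not use these cut-offs and are not affected.

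**What to change.** In section 9.2:
- Relate the 12-month change in platelet frataxin to the 12-month changes in SARA and in SCAFI as continuous variables.
- Define SCAFI once, consistently with section 6.1: Z-scores, mean or sum stated, reference values stated, and every component signed so that higher is better.
- Report Barthel and SF36 changes in points as supporting results. Name the SF36 score used, and note that Barthel still cannot rise from its maximum.
- If a responder analysis is kept, state the combination rule, set cut-offs in scale points, and show Barthel and SF36 response only for patients with room to improve.

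The cost is wording: sections 3.4 and 6.2 already schedule all these measurements at baseline and 12 months. The downside is that slopes or correlations replace a single odds ratio.
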